8.6.2 Estimands framework for secondary outcomes

For all secondary outcomes other than death, the same estimands framework will apply; if death occurs prior to any follow-up time, the outcome data that would have been collected will be deemed as non-existent data.

For death as an outcome, the treatment policy and principal stratum approaches will be used.

8.6.3 Approach to handling missing data for secondary outcomes

For all PROM secondary outcomes, physical activity secondary outcomes, sleep secondary outcomes, CK and CRP, multiple imputation across time points of data collection will be performed. Sensitivity analyses including observed and imputed data will be performed according to the estimands framework and general principles described above.

It is assumed that there will be no missing data for blood loss during surgery, duration of surgery, and length of hospital stay.

8.6.4 Sensitivity analyses for secondary outcomes

Sensitivity analyses with adjustment for unbalanced baseline characteristics, and using a mixed model with random effect on surgeon, will be performed for all continuous secondary outcomes, and for the number of nights in hospital.

8.6.5 Supplementary analyses

For all continuous secondary outcomes collected at more than one post-randomisation time point, a mixed model will be performed with a random effect on participant, including data collected at all time points. The interaction between treatment and time points will be reported with a two-sided 95% confidence interval and global p-value. These models will be performed for the treatment policy and principal stratum approaches.

8.7 Other analyses

No subgroup analyses are planned.

8.8 Interim analyses

No interim analyses are planned.

8.9 Adverse events analyses

SAEs will be reported descriptively by treatment as received (with footnotes to indicate where treatment received was not as allocated).

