2 ASSESSMENT AND MANAGEMENT OF RISK

All three surgical approaches (PA, PSPA, and SPAIRE) are already being used in the clinical setting. However, the use of the SPAIRE approach for THR using robotic assistance is currently limited, and extending this trial to include other sites with a MAKO robot would require training for both the PSPA and SPAIRE approach. This would include the inherent learning curves associated with adopting new technology and surgical methods. Therefore, the trial will be restricted to a single centre of excellence, where the MAKO robotic-guidance system is used in routine THR surgery, and all the surgical procedures that will be used in this trial have also been performed in routine THR surgery, both without and with robotic guidance. As such, the trial is considered to pose a risk no greater than standard medical care in this setting.

All three interventions are based on the standard PA approach, which means that it is possible to convert a PSPA or SPAIRE approach to a standard PA if required during surgery - a risk mitigation option which is available in standard care as well as in this trial.

A robust safety reporting procedure will be implemented (see section 7) such that adverse events will be detected and managed appropriately, according to established standard operating procedures.

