- To compare differences between (i) PSPA vs PA and (ii) SPAIRE vs PA in terms of pain medication used in addition to the standardised prescribed post-surgery medication, immediately post-surgery and 6 week post-operatively.
- To evaluate safety of PSPA and SPAIRE approaches with respect to the PA via recorded adverse events from the day of surgery until 12 months (52 weeks) post-operatively via medical notes and post-operative follow-up at 6 weeks, 6 months (26 weeks), and 12 months (52 weeks).

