5.2 Surgical expertise

It is a prerequisite that all treating surgeons listed on the trial delegation log have been trained to use the MAKO system, have performed a sufficient number of robotic-assisted THR procedures outside of the trial, and are familiar with the technique.

Surgeons will only be eligible to perform trial cases when they have completed the MAKO hip training course (Stryker will provide evidence to the trial team), have performed at least 12 MAKO hip cases outside of the trial, thus completing the learning curve for the MAKO robot, and they and the CI are confident that they are familiar with the technique.

Because participants in all three groups are receiving a version of the posterior approach with or without tendon preservation, if there is a clinical need to release more tendons to perform surgery safely this can be undertaken by the operating surgeon. The most common reason for conversion is if surgical exposure is insufficient and further tendon release is required to improve visualisation of the acetabulum to enable preparation and implantation of the acetabular component. This is likely to take the form of releasing one or two further tendons to improve surgical exposure. The data of any conversions will be collected; treatment switching will be accounted for using sensitivity analyses as per the estimands framework.

Surgery will be performed by seven Consultant orthopaedic surgeons in the Exeter hip unit who all have a similar experience of all three THR approaches and also the use of the MAKO robot. Only these named surgeons will perform the surgery and we do not anticipate any new surgeons joining the Research Team during the trial. The clinical team feel that there is minimal variability between

surgeons with regard to their ability in performing all three THR interventions, in terms of their patient outcomes as highlighted in the National Joint Registry.

5.3 Group 1 – THR with the standard PA and robotic guidance (Control Group)

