Participants will receive a THR using the PA in which three tendons are released to access the hip joint (piriformis, obturator internus, and obturator externus). An attempt is routinely made to repair these tendons after implantation of the hip replacement components. This is the current approach used in the majority of THR procedures in the UK. Robotic guidance using the MAKO robotic system will ensure that the acetabular cup component is accurately positioned in the surgically planned position during surgery.

5.4 Group 2 – THR with the PSPA and robotic guidance (Intervention Group A)

Participants will receive a THR using the PSPA in which two tendons are released to access the hip joint (obturator internus and obturator externus). These are repaired once the hip replacement components have been implanted. This approach is the most commonly used approach by surgeons in Exeter currently. This approach has been previously shown in an RCT to limit access and visibility of the hip joint compared with the PA and presents a greater challenge in accurately positioning the acetabular component [21]. Robotic guidance using the MAKO robotic system will ensure that the acetabular cup component is accurately positioned during surgery.

5.5 Group 3 – THR with the SPAIRE approach and robotic guidance (Intervention Group B)

Participants will receive a THR using the SPAIRE approach in which only one tendon is released to access the hip joint (obturator externus). This tendon is repaired once the hip replacement components have been implanted. This approach has been previously used but limits access and visibility of the hip joint, compared with both the PA and PSPA, and presents a greater challenge in accurately positioning the acetabular component. Robotic guidance using the MAKO robotic system will ensure that the acetabular cup component is accurately positioned during surgery.

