6.7 Trial assessments

6.7.1 Schedule of events

	Time point								
	Pre-op			Post-op					
Assessment/visit	Screening	Pre-op assessment (baseline)	7 days prior to surgery (Research Team)	24 hours prior to surgery (Surgeon & theatre staff)	Day 0/1 (inpatient)	Notes review after discharge	6 weeks (+/- 2 weeks)	6 months (26 weeks) (-4 weeks/+12 weeks)	12 months (52 weeks) (-4 weeks/+12 weeks)
Check eligibility and provide PIS	Х								
Confirm inclusion/exclusion criteria		Х							
Consent		Х							
Demographic data (name, DOB, sex of patient, height, weight, BMI, ethnicity), any existing comorbidities, and contact details		X							
Blood biomarkers – CK and CRP		Х			Х		Х		
Activity monitor issued in clinic and prepaid returns envelope provided		X					X		
PROMs – OHS, LEFS, EQ-5D-5L in clinic		Х							
Randomisation			Х	Х					
Check pre-operative imaging has been requested by surgeon (imaging to be done within 3 months of surgery date)		X							
Peri-operative data: length of stay ¹ , surgery time, blood loss, conversion of allocated randomisation approach ²						X			
PROMs – OARS, OACS, OHS, LEFS, EQ-5D-5L, SAPS in clinic							X		
Activity monitor issued via post and prepaid returns envelope provided								Х	Х
PROMs – OHS, LEFS, EQ-5D-5L, SAPS remotely								Х	Х
Additional analgesia use							Х		
Safety reporting – AEs and SAEs					Х	Х	Х	X	Х
Additional surgical procedures								X	Х
¹ Length of stay is recorded at time of discharge, i.e. converted to another during surgery (SPAIRE to PS	number of n PA or PA; or	ights a participa PSPA to PA).	int stays in	hospital post-	surgery. ² Co	nversion of a	pproach recor	ds if the intende	ed approach is

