8.6 Analyses of secondary outcomes

8.6.1 General principles

For the secondary outcomes, the threshold for significance will be (two-sided) 0.025, and a global p-value comparing effects across all three treatment arms will be reported in addition to two-sided 95% CIs for all three pairwise comparisons; no corrections will be made for multiple testing, but p-values will be interpreted in the light of the number of comparisons being made.

Continuous PROM outcomes (OACS, SAPS, OHS, LEFS, EQ-5D-5L) will be analysed using the same principles as for OARS; OHS, LEFS and EQ-5D-5L will be collected at baseline, so baseline scores will be adjusted for. In addition, the four physical activity outcomes, the two sleep outcomes and the biomarkers, CK and CRP, will be analysed using these principles.

Time to discharge from hospital is to be measured in terms of the number of nights spent in hospital. It is anticipated that he majority of participants will be discharged on the day of surgery, so the number of nights spent in hospital will be 0. The number of nights spent in hospital will be reported descriptively by participant group, and also analysed using a negative binomial model, which will account for zero-inflation, with adjustment for minimisation variables.

Analgesia outcomes will be modelled using appropriate methods (i.e. linear regression modelling for dose outcomes and logistic regression modelling for binary outcomes).

Deaths will be reported descriptively, by allocated group, for the full period of the trial from randomisation to 12-month follow-up, and for the following time periods:

- Post-randomisation and pre-operative
- Peri-operative (within 24 hours of surgery)
- 1 day to 6 weeks post-operative
- More than 6 weeks to 52 weeks post-operative

Furthermore, the odds ratio for death (at any time during follow-up to 52 weeks post-operative) comparing PSPA vs PA, SPAIRE vs PA, and SPAIRE vs PSPA will be reported with two-sided 95% confidence intervals.

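### Section 8.9 groups serious adverse events only by approach received, so SAEs after converted SPAIRE and PSPA operations count under a less sparing approach, often the PA control

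*Protocol*

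**What the plan says.** - **SAE grouping.** Protocol section 8.9 is a single sentence: "SAEs will be reported descriptively by treatment as received (with footnotes to indicate where treatment received was not as allocated". No SAE table by allocated group is stated anywhere in the protocol.
- **Safety objective.** Section 3.2: "To evaluate safety of PSPA and SPAIRE approaches with respect to the PA via recorded adverse events".
- **Direction of conversion.** Section 2: "it is possible to convert a PSPA or SPAIRE approach to a standard PA if required during surgery". The footnote to the schedule of events in section 6.7.1 lists SPAIRE converted to PSPA or PA, and PSPA converted to PA. It lists no conversion out of PA.
- **Cause of conversion.** Section 5.2: "The most common reason for conversion is if surgical exposure is insufficient and further tendon release is required". On its extent, the same section adds: "This is likely to take the form of releasing one or two further tendons to improve surgical exposure". Section 5.5 says of SPAIRE that it "limits access and visibility of the hip joint, compared with both the PA and PSPA", and section 5.4 says that PSPA gives less access than PA.
- **Deaths.** Section 8.6.1: "Deaths will be reported descriptively, by allocated group, for the full period of the trial". Section 7.4 requires every death after randomisation to be reported as an SAE.
- **Efficacy.** Section 8.5.2 uses a treatment-policy approach when the treatment received differs from the allocation.

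**The concern.** As-received safety tables are a familiar convention, and do little harm when switching is rare, symmetric or unrelated to risk. Here the switching is asymmetric and is a consequence of the allocated technique: the less sparing the approach, the better the exposure and the less reason to convert. Section 6.7.4 also collects events that occur during surgery. An injury during an attempted SPAIRE operation that is then converted to PA would be tabulated under PA.

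Two things follow. The SPAIRE and PSPA columns lose the operations that could not be completed as planned, and a less sparing column gains them along with their SAEs. The randomised comparison that section 3.2 asks for, PSPA and SPAIRE against PA, is then not preserved in the only SAE analysis stated. A reader choosing an approach wants the risk of setting out to do it, including the chance of having to convert.

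**Working it through.** **1. Groupings side by side**

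| Item | Section | Grouping |
|---|---|---|
| Primary outcome | 8.5.2 | allocated (treatment policy) |
| Deaths | 8.6.1, 8.6.2 | allocated; treatment policy and principal stratum |
| SAEs, which include deaths (7.4) | 8.9 | received |

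A death after a SPAIRE-to-PA conversion is counted under SPAIRE in the death table and under PA in the SAE table. A death between randomisation and surgery is reportable as an SAE under 7.4 but has no approach received, so 8.9 gives it no column.

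**2. The plan's own figures.** The protocol states no SAE rate, conversion rate or safety sample size. Only the arm size is usable (section 8.1): 321/3 = 107; 107/0.95 = 112.6, rounded up to 113; 113 x 3 = 339. So n = 113 per arm.

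**3. Assumed inputs (not in the protocol).** SAE risk b = 5% in PA operations; u = 5% in unconverted SPAIRE and PSPA operations; h = 20% in converted operations. Converted to PA: c_S = 10% of SPAIRE and c_P = 5% of PSPA, which is 11.3 + 5.65 = 16.95 operations.

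**4. By allocation**
- PA: 5.0%
- PSPA: 0.95 x 5% + 0.05 x 20% = 5.75%
- SPAIRE: 0.90 x 5% + 0.10 x 20% = 6.5%
- SPAIRE minus PA: +1.5 points

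**5. As received**
- PA: (113 x 0.05 + 16.95 x 0.20)/(113 + 16.95) = 9.04/129.95 = 7.0%
- PSPA and SPAIRE: 5.0% each (unconverted operations only)
- SPAIRE minus PA: -2.0 points

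**6. The same mechanism in whole patients.** Take SAEs by allocation of PA 6/113 (5.3%), PSPA 7/113 (6.2%) and SPAIRE 8/113 (7.1%). Let 11 SPAIRE operations (3 with an SAE) and 6 PSPA operations (2 with an SAE) be converted to PA. The as-received table reads PA 11/130 (8.5%), PSPA 5/107 (4.7%), SPAIRE 5/102 (4.9%).

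**7. How far this depends on the assumptions**
- *Risk after conversion.* With u = b, SPAIRE minus PA is c_S(h - b) by allocation and -(c_S + c_P)(h - b)/(1 + c_S + c_P) as received. The signs are opposite whenever h > b. With h = b both are zero and nothing reverses.
- *Range.* With b from 3 to 8%, h from 10 to 30%, and conversion from 2%/1% to 20%/10% (SPAIRE/PSPA), SPAIRE minus PA runs from +0.04 to +5.4 points by allocation and from about -0.1 to -6.2 points as received. All 36 combinations reverse, but the formulas show that they must once u = b and h > b. This is no independent evidence.
- *Risk without conversion.* Counting SPAIRE conversions only, received PA is (b + c_S h)/(1 + c_S): 0.06/1.05 = 5.7% at 5% converted and 0.07/1.10 = 6.4% at 10% converted. Reversal stops once u for SPAIRE reaches these values, so at about 6 to 6.5%. With the PSPA conversions of step 3 added, the limit is the 7.0% of step 5.
- *Destination.* If every SPAIRE conversion stops at PSPA, received PA is (5.65 + 1.13)/118.65 = 5.7%, PSPA is (5.37 + 2.26)/118.65 = 6.4% and SPAIRE is 5.0%. SPAIRE against PA still reverses (-0.7 points) because of the PSPA-to-PA conversions. PSPA against PA does not: it is +0.75 points by allocation and +0.7 as received.

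**The case against.** The strongest reply has five parts.

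1. **The reversal is built in.** It needs assumed conversion and SAE rates and equal risk in unconverted operations and PA. This stands: the reversal is an illustration, not a forecast.
2. **Sampling error is larger than the shift.** With 113 per arm and the step 4 risks, the 95% half-width for SPAIRE minus PA is 1.96 x sqrt(0.05 x 0.95/113 + 0.065 x 0.935/113) = 6.1 points. Section 8.9 is descriptive, and the progression considerations in section 12.2 do not name SAE rates. This stands and limits the severity. It does not justify a grouping whose expected error has a known direction when converted operations are riskier.
3. **Conversions are disclosed.** The footnotes let a reader trace moved cases, and conversions and their reasons are recorded. This softens the problem, but the counts and denominators remain as received.
4. **Not every conversion reaches the control.** One further tendon released in a SPAIRE operation makes it a PSPA. This stands, and the point is worded accordingly.
5. **Deaths are already compared by allocation.** Section 8.6.1 does so, with odds ratios, and allocation is the natural grouping for a period that starts before surgery. This stands: the gravest harm is covered.

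A reader might also infer that the SPAIRE and PSPA columns would hold only uncomplicated operations. The protocol does not support this: the main stated reason for conversion is poor exposure, not a complication, so those columns hold unconverted operations. Nor does the silence of 8.9 on non-serious adverse events show that they will go unanalysed. The trial summary commits to reporting related adverse events, and table content of that kind is commonly left to the SAP.

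**Conclusion.** The point holds as a flaw in the stated grouping, and it should be fixed. Section 8.9 makes treatment received the only basis for the SAE comparison, while the protocol's own account of conversion makes that basis depend on the allocated technique. The direction of the bias, in favour of the tendon-sparing approaches, rests on converted operations carrying excess risk. That is plausible, but the protocol does not state it. The size is unknown: +1.5 points turning into -2.0 is one illustration, and there is no reversal under the limits in step 7.

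A reader might conclude that the plan will reverse the safety result. The documents do not support that, because they give no conversion rate, SAE rate or risk after conversion. The one-way pattern concerns conversions during surgery; section 3.1.1 also allows for treatment received in error, which could run in any direction. The different groupings for deaths and SAEs are not a contradiction in themselves, but they allow the same death to sit in different columns of two safety tables.

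**What to change.** Reword section 8.9 so that the main safety table gives SAE counts and percentages by allocated group. It should include any reportable death between randomisation and surgery, so that it agrees with sections 7.4 and 8.6.1 and with the treatment-policy approach in 8.5.2. Restricting it to operated participants would drop those deaths.

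Keep the as-received table as a supplement, with converted cases shown separately by allocated arm together with their SAEs. Pairwise risk differences with confidence intervals are optional; the table can stay descriptive.

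The cost is a changed sentence and one more descriptive table. No new data are needed, since allocation, conversions and their reasons are already recorded. The change should be made before unblinded results are seen.

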8.10 Mediation analyses

The potential for mediation effects of allocated treatment on OARS at 6-week follow-up, via an inflammatory effect measured by CRP and CK at day 0/1 follow-up, will be investigated using causal mediation modelling, using observed data only.

8.11 Other statistical considerations

Any amendments to the statistical analysis plan following initial approval by the TSC and sign-off by the senior statisticians and CI will be documented.

9 DATA MANAGEMENT

The handling, and storage of all personal data collected during the trial will comply with the Data Protection Act 2018 and the General Data Protection Regulation.

9.1 Data collection tools and source document identification

The primary data sources will be the participant's electronic medical notes on EPIC and trialspecific electronic Case Report Forms (eCRFs). Data will be collected contemporaneously through the trial on eCRFs with information extracted from source data within the participant's clinical records. PROMs data will be recorded pre-operatively, and at 6 weeks, 6 months (26 weeks) and 12 months (52 weeks) post-operatively with direct participant input onto REDCap. This is with the exception of paper PROMs should the participant opt for this, and the site Research Team will

transcribe the PROMs data onto REDCap once received from the participant. Results from blood biomarker collection pre-operatively and at 6 weeks post-operatively will be obtained from participant medical notes on EPIC and transcribed by a member of the site Research Team onto REDCap. Physical activity monitoring data will be uploaded and stored locally, and transferred pseudonymously to members of the University of Exeter Research Team (Co-CI) for processing.

Participants will be identified by a trial number allocated at the point of enrolment which will ensure anonymity of data recorded electronically. This will be the same as their randomisation number, however different from their participant screening number.

Sites will be required to answer data queries raised by ExeCTU within a timely manner within the trial database. A data cleaning work instruction will be provided to sites.

A separate Electronic Data Capture (EDC) project will be used to store personal identifiable data (i.e. names, addresses, email addresses, telephone numbers) that will be separate from the research data. Personal data will be collected to facilitate the sharing of newsletters and trial results and assist with retention and follow-up activities. Access to the contact details will be restricted to individuals authorised by the CI. All EDC system users will require individual log-in credentials and authorisation from an approved member of the trial management team before access is granted. The EDC system will incorporate role restriction such that individual users will only be able to access and enter or edit data as their individual permissions allow. The ExeCTU trial management team will run regular reports for missing data and remind sites at least monthly to enter data that is expected and document any reasons for missing data.

9.2 Data handling and record keeping

A Data Management Plan (DMP) will be drafted prior to starting participant recruitment and will be updated throughout the trial as appropriate. Working instructions will be provided to the RDE site on record keeping and data entry processes. Electronic systems will be validated, tested and documented before starting recruitment. The DMP and validation documents will be available upon request to ExeCTU.

